4 STATISTICAL/ANALYTICAL ISSUES

No formal statistical analyses will be performed. All variables will be summarized using descriptive statistics; there will be no inferential analyses. For continuous variables, summary statistics (number of available observations, mean, standard deviation, minimum, lower quartile, median, upper quartile and maximum) will be tabulated. Categorical variables will be summarized by the number of patients and the percent of patients in each category. For time to event variables, medians derived using Kaplan-Meier estimates and corresponding 95% CIs will be presented. Supporting Kaplan-Meier plots will be presented.

Data from patients who prematurely withdraw from the study will be analyzed up to the final visit attended.

4.1 Adjustments for covariates

No formal statistical analyses will be performed and consequently there will be no adjustment for covariates.

4.2 Handling of dropouts or missing data

All available data will be used for analysis.

Missing data of the variables will not be substituted. However, imputations of missing values as described in this section will be done in order to use the available data as much as possible, eg, imputations for missing or partial values for dates will be applied to calculate derived variables or to determine prior and concomitant medication

With respect to ADRs, events with missing information about action taken regarding UCB suspected drug status are regarded as ADRs leading to premature discontinuation. Events with no

answer to the question “Seriousness indicators: Is the event/reaction serious?” will be regarded as serious.

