3.10.10 Discontinuation of LCM due to an ADR

A patient who discontinued LCM due to an ADR is defined as a patient who prematurely terminated from the study and the primary reason for premature study termination = “ADVERSE DRUG REACTION”.

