3.10.15 Adverse Drug Reactions

Adverse drug reactions will be documented during the study only. Since an ADR is an adverse event related to the medication to be investigated (LCM), all reported ADRs are considered treatment-emergent and will be included in the analysis.

An ADR with action taken regarding UCB suspected drug reported as “Permanently discontinued” will be regarded as an ADR leading to discontinuation of LCM.

Adverse drug reactions that have the question “Seriousness indicators: Is the event/reaction serious?” answered “yes” are considered as serious.

Note AESIs are collected as ADRs and will be treated as ADRs in the analysis.

Other significant ADRs will be summarized.

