10 SAFETY ANALYSES

All statistical analyses for the safety variables will be performed for the SS and the modified FAS in an exploratory manner. Exposure data will be listed in the SS and adverse drug reactions will be listed in the ES.

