10.1 Extent of exposure

The following information about intake of LCM during the study will be summarized:

- Duration of exposure (days) including patient years of exposure
- Maximum daily dose (mg/day)
- Modal daily dose (mg/day)
- LCM ongoing at the end of the study (yes, no)

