10.2 Adverse events

Adverse drug reactions will be coded for analysis with version 16.1 of MedDRA. Note that AESIs will be collected as ADRs and consequently AESIs will be included in the summary tables and listings for ADRs.

Adverse drug reactions that occur during this study will be presented by MedDRA SOC and PT in a frequency table giving the number and percentage of patients experiencing each event at least once as well as the number of events. For the number and percentage of patients, patients

with multiple ADRs will be counted only once within each PT and SOC. All table summaries will be sorted alphabetically by SOC and by decreasing relative frequency of each PT within SOC.

The following tabular summaries will be presented.

- Adverse drug reactions
- Serious ADRs
- Non-serious ADRs
- Non-serious ADRs above reporting threshold of 5% (as per the requirements for the EU agency)
- Adverse drug reactions leading to discontinuation
- Deaths
- ADRs by dose at onset (dose categories will be agreed during the DEM to obtain a sensible distribution)
- Other significant ADRs

An overall summary table of all ADRs will be presented summarizing the ADR categories given above (except non-serious ADRs above reporting threshold).

A listing of all ADRs will be provided as follows:

- Individual patients (identified by patient numbers) experiencing a given ADR grouped by SOC, High Level Term (HLT), PT, and severity.
- A glossary of all physician-reported terms, grouped by coded SOC, HLT, and PT. This table will serve as a glossary of PTs, showing which reported terms are summarized under each PT.

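### SAP 4.2 counts an ADR with missing action taken as leading to discontinuation even when the patient completed on lacosamide, so the safety table of such ADRs can contain false entries

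*SAP*

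**What the plan says.** SAP 4.2 sets the rule for a blank field: "events with missing information about action taken regarding UCB suspected drug status are regarded as ADRs leading to premature discontinuation". It makes no exception for completers and refers to no other data source. The same paragraph treats a blank seriousness field as serious.

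SAP 3.10.15 covers the filled field. Only an ADR for which the drug was permanently discontinued "will be regarded as an ADR leading to discontinuation of LCM". AESIs are handled as ADRs, so the rule reaches them too.

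The flag feeds one table in SAP 10.2, "Adverse drug reactions leading to discontinuation", and the matching line of the overall ADR summary. On the populations, SAP 10 says: "All statistical analyses for the safety variables will be performed for the SS and the modified FAS in an exploratory manner".

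The secondary variable on discontinuation due to an ADR comes from another source. SAP 3.10.10 requires that the patient "prematurely terminated from the study and the primary reason for premature study termination" is an adverse drug reaction. SAP 8.2.7 reports it for the Safety Set (SS), FAS and modified FAS with a Clopper-Pearson interval.

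Other parts of the plan establish whether a patient stopped LCM:

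- Protocol 8.2 withdraws a patient whose physician stops LCM.
- SAP 3.10.7 censors completers in the time-to-discontinuation analysis.
- SAP 3.10.14 takes actual dosing from the Drug Dosing Log and, where LCM is ongoing, the last administration date from the Study Termination CRF.
- SAP 10.1 tabulates whether LCM was ongoing at study end.

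**The concern.** A worst-case rule suits an unknown. For a patient who completed with LCM ongoing, the answer is not unknown: the dosing and termination records show that no ADR led to early discontinuation. The rule overrides those records because one field on a different form is blank.

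Blank fields are foreseeable. Protocol 10.1.7 has sites send the adverse event form even when data are lacking, and the ADR analysis draws on the global safety database that those forms feed.

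Tolerability is part of the secondary objective, and this table is one of the places where a reader looks for it. Protocol 11.3.4 describes the table as covering ADRs that led to withdrawal. A completer did not withdraw, yet SAP 3.9 declares no departure from the protocol's analyses. For completers the error runs only upward.

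**Working it through.** **Step 1: follow one patient through the plan.** Take a patient who completes with LCM ongoing and has one ADR with action taken left blank.

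| SAP section | Data used | Result for this patient |
|---|---|---|
| 4.2 and 10.2, table of ADRs leading to discontinuation | Action taken (blank) | Counted |
| 3.10.10 and 8.2.7, discontinuation due to an ADR | Termination status and primary reason | Not counted |
| 3.10.7, 8.2.1 and 8.2.2, time to discontinuation and retention | Dosing dates and completion status | Censored |
| 10.1, LCM ongoing at study end | Dosing and termination records | Yes |

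Only the first row uses action taken, and it is the only row in which this patient appears as a discontinuation.

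**Step 2: the plan's own figure.** The plan states no expected rate of ADR discontinuation and no rate of missing action taken. Its one design figure is the 93 evaluable patients in SAP 2.4. It reproduces: 1.96² × 0.60 × 0.40 / 0.10² = 92.2, rounded up to 93, and the half-width at 93 is 1.96 × √(0.24/93) = 0.0996. That number serves the precision of the responder rate. It is not the size of the SS.

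**Step 3: the denominator.** SAP 3.1 makes the analysis population the default denominator. The planned enrolment is 100. If all 100 receive LCM, which is an assumption, the SS has N = 100. The size of the modified FAS is not given. If it were 93, one patient would be 1/93 = 1.1 points.

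**Step 4: the size.** Let k be the patients with a true ADR discontinuation, and m the completers with LCM ongoing whose only flagged ADR has a blank action taken. Both are assumptions.

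- Table under SAP 4.2 as written: 100 × (k + m)/N
- Table with such completers excluded: 100 × k/N
- Excess: 100 × m/N, which is 1.0 point per completer at N = 100

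| k | m = 0 | m = 1 | m = 2 | m = 5 |
|---|---|---|---|---|
| 0 | 0% | 1% | 2% | 5% |
| 5 | 5% | 6% | 7% | 10% |
| 10 | 10% | 11% | 12% | 15% |

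The m = 0 column is both the correct result and the result when the field is complete.

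**The case against.** The strongest defence is that this is a prespecified worst-case convention, parallel to the rule for missing seriousness, which can overstate harm but never hide it. All analyses are descriptive, and the listings of ADRs and of premature terminations would let a reader spot a flagged completer. Sponsor follow-up of unclear ADR reports (Protocol 10.1.7) and the data checks (Protocol 12.1.2.2) may leave few blanks or none. This stands for patients who stopped LCM early or whose status is unknown, and it keeps the point minor. It fails for completers with LCM ongoing, because a convention for unknowns should not override a recorded fact.

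Three stronger readings are tempting, and the documents do not support them.

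- A reader might infer that the study's ADR-discontinuation rate is inflated. It is not. SAP 3.10.10 opens with "A patient who discontinued LCM due to an ADR is defined as a patient who prematurely terminated from the study", so a completer cannot enter it, and action taken plays no part. Retention and time to discontinuation do not use the field either.
- A reader might infer that this rule is the reason why the safety table and the secondary rate could disagree. It is only one possible reason. The table works from events and the secondary rate from the patient's primary reason for termination, so they can differ with no missing data at all. One example is LCM stopped for an ADR with another primary reason recorded.
- A reader might set the rule against "Missing data of the variables will not be substituted", also in SAP 4.2, and see a contradiction. The next sentence there allows the imputations that the section describes, and this is one of them.

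**Conclusion.** The point holds within a narrow scope. As SAP 4.2 is written, a patient who completed with LCM ongoing can be wrongly included in the table of ADRs leading to discontinuation and in its line of the overall ADR summary, for the SS and, where the patient qualifies, the modified FAS. No primary variable, secondary discontinuation rate, retention estimate or Kaplan-Meier analysis is touched.

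The size is 1.0 point per affected completer, resting on the assumption that all 100 planned patients are in the SS. With an assumed 5 true cases, 1 to 5 affected completers would move the table from 5% to between 6% and 10%. With complete action-taken data the effect is zero. The documents do not show which of these will apply. The point is minor, but the rule gives a wrong entry whenever the case arises.

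**What to change.** In SAP 4.2, replace the unconditional rule with an ordered one:

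1. Where action taken is missing, first consult the Drug Dosing Log and the Study Termination CRF.
2. If the patient completed the study with LCM ongoing, classify the ADR as not leading to discontinuation.
3. Keep the worst-case imputation only where LCM was stopped early or its status at study end is unknown.
4. Footnote the table and the overall summary with the number of events imputed.

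The cost is a few lines of SAP text and one extra program condition, and the count becomes slightly less conservative. The change will not force the table to agree with the secondary rate. It also still flags a patient who stopped LCM early for a non-ADR reason and has a blank field. The footnote lets a reader see how much of the table rests on imputation.

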4.2.1 Incomplete dates for medication and ADRs

In order to classify medication as prior or concomitant or to classify an ADR as treatment emergent, a complete date must be established. For the purposes of imputing missing components of partially-reported start and stop dates for medication use or ADRs, the algorithms listed below will be followed. Start and stop dates will be displayed as reported in the patient data listings (ie, no imputed values will be displayed in data listings).

- Missing start day but month and year present:

If the start of LCM occurred in the same month and year as the start of the medication or ADR, the start day of the medication or ADR will be assigned to the day of first administration of LCM.

Otherwise the start day will be set to the 1st day of the month.

- Missing start day and month but year present:

If the start of LCM occurred in the same year as the start of the medication or ADR, the start day and month will be assigned to the date of first administration of medication.

Otherwise the start day and month will be set to January 1st.

- Missing end day but month and year present:

The end day will be set to the last day of the month.

- Missing end day and month but year present:

The end day and month will be set to the date of study termination. However, if the study termination year is greater than the medication or ADR end year, the day and month are to be set to December 31st.

- Missing year but month or day and month present:

The rules as described in Section 4.2.2 will be followed.

If the end date is completely missing, then the medication or ADR are assumed to be ongoing.

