4.2.2 Definition of concomitant medication in case of missing dates

The following rules for classifying medication as prior or concomitant will be applied in the case of completely missing stop and/or start date information:

Table 4-1: Rules for assignment of medication in case of missing start and/or stop dates			
Start date	Stop date	Prior medication	Concomitant medication
Missing	Missing	Yes	Yes
Missing	Before start date of LCM	Yes	No
Missing	After start date of LCM	Yes	Yes

Table 4-1: Rules for assignment of medication in case of missing start and/or stop dates

Start date	Stop date	Prior medication	Concomitant medication
Before or on start date of LCM	Missing	Yes	Yes
After start date of LCM	Missing	No	Yes

In patient data listings, dates will be displayed as reported.

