6.4 Prior and concomitant medications

The number and percentage of patients who used prior and concomitant medications (including chemotherapy and AEDs) will be summarized according to the anatomical therapeutic class main group, the therapeutic subgroup, and the generic drug name.

Prior medications are those medications started before the first dose of study drug. Medication taken after the first dose of study medication will be regarded as concomitant medication whether the start date is before, after or on the date of the first dose of study medication. Lifetime AEDs are AEDs with an end date before the first dose of study drug.

The core AED will be summarized separately using the “Core AED?” question on the CRF to select the relevant medications. The core AEDs are the AEDs that the patient is receiving at Baseline.

The number and percentage of patients according to Core AED therapies will be summarized according to preferred term combination.

The number and percentage of patients who had prior or concomitant radiotherapy will be summarized. The total dose in gray (Gy) and number of fractions will be summarized as continuous variables.

Rules for defining concomitant medications with missing dates are provided in [4.2.2](#).

All prior and concomitant medication and radiotherapy will be listed.

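### The partial-date rule in SAP 4.2.1 ignores the stop date, so some medications that ended before lacosamide become neither prior nor concomitant

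*SAP*

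**What the plan says.** SAP 4.2.1 completes partial medication dates so that each drug can be sorted into prior or concomitant use. It has two branches for the start date.

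- Day missing: "If the start of LCM occurred in the same month and year as the start of the medication or ADR", then "the start day of the medication or ADR will be assigned to the day of first administration of LCM". Otherwise the first of the month is used.
- Day and month missing: if the year is the year of LCM start, "the start day and month will be assigned to the date of first administration of medication". Otherwise 1 January is used.

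A stop date without a day is completed separately: "The end day will be set to the last day of the month".

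SAP 6.4 supplies the classification. "Prior medications are those medications started before the first dose of study drug", and "Medication taken after the first dose of study medication will be regarded as concomitant medication". The summary built on these definitions includes chemotherapy and AEDs.

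Table 4-1 in SAP 4.2.2, titled "Rules for assignment of medication in case of missing start and/or stop dates", holds further rules, but the text above it says that they "will be applied in the case of completely missing stop and/or start date information". SAP 4.2.3 has a general rule that takes the earliest possible date, and it lists medication dates among its exceptions.

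**The concern.** A recorded stop before the first LCM dose is enough to show that a drug was prior: whatever its exact start, it began before LCM. The imputation does not use that fact. It can place the start after the stop, which is an impossible sequence, and the drug then fails both tests in SAP 6.4.

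The plan also contradicts itself. If nothing is known about the start and the stop is before LCM, Table 4-1 gives prior yes and concomitant no. If the site adds the correct year, and that year is the LCM year, the drug disappears from both categories. More information produces a worse answer.

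Partial dates are plausible here. The protocol's schedule (Table 15-1, footnote d) asks for tumor management and other relevant medications over the previous 8 weeks plus relevant earlier history, so some dates will come from recall or old records. In a single-arm study without covariate adjustment, readers rely on an accurate description of earlier therapy.

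**Working it through.** The plan states no figure for this point, so there is none to reproduce. The check applies the rules as written.

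**Inputs.** Imputed start and stop follow SAP 4.2.1, with the year-only branch read as LCM. Prior means imputed start < first LCM dose. Concomitant means stop > first LCM dose, or ongoing (both SAP 6.4). Assumed for illustration: LCM start 20 Sep 2016 and study termination 20 Mar 2017.

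| Recorded start | Recorded stop | Imputed start | Stop used | Result |
|---|---|---|---|---|
| Sep 2016 | 10 Sep 2016 | 20 Sep 2016 | 10 Sep 2016 | neither |
| 2016 | 10 Mar 2016 | 20 Sep 2016 | 10 Mar 2016 | neither |
| 2016 | Mar 2016 | 20 Sep 2016 | 31 Mar 2016 | neither |
| Aug 2016 | 10 Sep 2016 | 1 Aug 2016 | 10 Sep 2016 | prior |
| 2015 | 10 Mar 2016 | 1 Jan 2015 | 10 Mar 2016 | prior |
| 1 Sep 2016 | 10 Sep 2016 | 1 Sep 2016 | 10 Sep 2016 | prior |
| Sep 2016 | Sep 2016 | 20 Sep 2016 | 30 Sep 2016 | concomitant only |
| 2016 | 2016 | 20 Sep 2016 | 31 Dec 2016 | concomitant only |
| 2016 | ongoing | 20 Sep 2016 | none | concomitant only under SAP 6.4; prior and concomitant under Table 4-1 |

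In the three failing rows the imputed start falls after the stop by 10, 194 and 173 days.

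**Enumeration.** Take each day of 2016 as the LCM start and each complete stop date before it.

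- Year-only start, stop earlier in the same year: 0 + 1 + … + 365 = 365 × 366 / 2 = 66,795 combinations. All 66,795 end as neither.
- Day-missing start, stop earlier in the same month: a month of d days gives d(d − 1)/2 combinations, so 7 × 465 + 4 × 435 + 406 = 3,255 + 1,740 + 406 = 5,401. All 5,401 end as neither.

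These counts show that the failure is systematic once its conditions are met. They do not say how often the conditions are met.

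**Is there a rescue elsewhere?** Table 4-1 does not apply to a partial start, and SAP 4.2.3 leaves medication dates out of its earliest-date rule. No other section addresses these records.

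**With the correction.** If a stop before LCM triggers the earliest date consistent with the partial start, the three failing rows receive starts of 1 Sep, 1 Jan and 1 Jan 2016 and become prior only. This agrees with Table 4-1 for a wholly missing start. The imputed dates and SAP 6.4 results of the other six rows do not change.

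**The case against.** The strongest reply is that this is an edge case with little reach, and much of that stands.

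- **AEDs.** A reader might infer that washed-out AEDs vanish from the analysis. They do not. SAP 6.4 defines lifetime AEDs by end date alone, and core AEDs come from a question on the case report form. The loss for AEDs is confined to the prior-medication summary.
- **Subgroups.** A reader might infer that the prior tumor treatment subgroups in SAP 4.8, in which both primary variables are summarized, are misassigned. The documents do not establish this. SAP 4.8 does not say how the subgroups are derived, and the protocol's Table 15-1 collects tumor management as an item separate from AEDs and other medications. SAP 6.4 counts chemotherapy among the medications, so the effect is possible but conditional.
- **Drugs that continued into LCM treatment.** A reader might wish to class every partial start in the LCM month or year as both prior and concomitant. With a missing stop, Table 4-1 already gives that answer. With a known stop on or after LCM, a year-only start does not show which came first, so the choice is a convention and not an error.
- **The boundary.** Table 4-1 counts a start on the day of LCM as prior, whereas SAP 6.4 requires a start before the first dose. A programmer who borrowed the Table 4-1 boundary would class the failing records as prior. But that row covers only missing stops, and the start would still fall after the stop.
- **Narrowness.** The day-missing branch fails only for a drug both started and stopped in the LCM month, before LCM. The year-only branch is wider, but its text does not name LCM.

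All analyses are descriptive, and listings show dates as reported, so affected records stay visible. None of this removes the impossible date order or the missing classification.

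**Conclusion.** The error is real and limited. As written, SAP 4.2.1 and 6.4 together leave a medication unclassified when its start is partial within the LCM month (day missing) or the LCM year (day and month missing) and its recorded or imputed stop is before the first LCM dose. This rests on the strict wording of SAP 6.4 and, for the year-only branch, on reading the date as that of LCM.

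The certain consequence is an undercount in the prior-medication summary, chemotherapy and AEDs included. The documents give no count of such records. For scale only: with the planned 100 patients as denominator, each patient whose only record of a drug is of this kind lowers that drug's prior-use percentage by 1/100, or 1 percentage point. Five to 10 such patients, a pure assumption, would lower it by 5 to 10 points. The overall responder and PGIC results do not use these dates and do not change.

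**What to change.** Add to SAP 4.2.1, for medications:

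- No imputed start may fall after the recorded or imputed stop date.
- If the stop is before the first LCM dose, impute the start as the earliest date consistent with the partial date, and class the medication as prior only.

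Two wording points should be settled in the same edit. The year-only branch should name LCM, as the day-missing branch does. SAP 6.4 and Table 4-1 should use one boundary for a start that falls on the day of LCM. The date-order rule works with either choice, but the choice decides how a start imputed to that day is classed when the stop is later, so it should be stated.

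It would also help to say in SAP 4.8 whether the prior tumor treatment subgroups use these date-derived flags.

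The cost is a few sentences and one programming check for starts later than stops. No new data are needed.
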